### **Pregnancy outcomes (PO)**

POs are of interest because the target population includes women of child-bearing age. The overall pregnancy data generated so far from large clinical trials, post marketing passive surveillance (including the pregnancy registry set up in the UK and in the United States from 2007 to 2015 [[GlaxoSmithKline Biologicals Clinical Study Report 201337](#)]) and from the epidemiological study EPI-HPV-018 [[Baril, 2015](#)], are reassuring for the vast majority of women and their offspring, if vaccination occurred during pregnancy [[Lopez-Frauqued, 2017](#)]. Data from the observational epidemiology study EPI-HPV-018 showed no increased risk of spontaneous abortion (SA), among women exposed to a single dose of *Cervarix* around 6 or 12 weeks before and up to four weeks after the first day of their Last Menstrual Period (LMP), when compared to the control group [[Baril, 2015](#)]. Also, data regarding the potential risk of SA, in the rare case that a woman received two doses of *Cervarix* in the same time period was found to be inconclusive. Considering all data available and the inconsistency in findings concerning the risk of SA when exposed to two doses, women who are pregnant or trying to become pregnant are advised to postpone vaccination until completion of pregnancy. Also, there is no evidence that suggests vaccination with *Cervarix* alters the risk of abnormal outcomes including birth defects in neonates.

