### **9.9.3. Analysis for Secondary endpoints**

The occurrence of serious AEFIs will be assessed throughout the entire follow-up period in all enrolled subjects. Serious AEFIs will be further evaluated for their clinical relevance and relationship to vaccination.

The occurrence of pIMD(s) will be collected and summarized through the entire follow-up period in all enrolled subjects.

The PO and congenital anomalies will be summarized when *Cervarix* is administered within 60 days before pregnancy onset or any time during pregnancy. In addition, the PO

will be summarized by the time of the vaccination, such as vaccination before the pregnancy, vaccination during the first trimester of the pregnancy, vaccination during the second trimester of the pregnancy etc.

All secondary endpoints (serious AEFIs, pIMDs and POs) will be summarized by percentage of subjects reporting the endpoint with exact 95% CI.

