### **9.12. Limitations of the research methods**

The study population may not be representative of the entire population eligible for vaccination. This is because the administration of vaccine will not be part of the universal vaccination programme but performed on a voluntary basis as per standard practice in vaccination centres. In particular, there may be an uneven age distribution of the study participants.

The study is descriptive and is not designed to assess an epidemiological association between a given adverse event and vaccination.

The sample size of approximately 3000 subjects meets the requirements of the Chinese regulation. Due to the low incidence of pIMDs (generally < 40 per 100,000) in adolescent girls and young women and the limited number of expected exposure to *Cervarix* during pregnancy, the study will be limited for the detection of these rare events.

The study will only enroll subjects vaccinated with *Cervarix* and thus will not have a control group. Therefore, the observed frequency of AEFI will be interpreted in terms of safety data generated in clinical trials, post-licensure epidemiological studies and background incidence rates reported in the literature.

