5. STATISTICAL ANALYSES

That standard data derivation rules and stat methods are described in section 10. All analyses will be performed on the exposed set.

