5.4.2. Analysis for Secondary endpoints

The analysis will be based on the ES.

The occurrence of serious AEFIs will be assessed throughout the entire follow-up period. Serious AEFIs will be further evaluated for their clinical relevance and relationship to vaccination.

The percentage of subjects with serious AEFI occurring within the 30-day (Day 1-30) follow-up period will be tabulated with exact 95% CI after any dose.

The occurrence of pIMD(s) will be collected and summarized through the entire follow-up period in all exposed subjects.

The PO and congenital anomalies will be summarized when *Cervarix* is administered within 60 days before pregnancy onset or any time during pregnancy. In addition, the PO will be summarized by the time of the vaccination, such as vaccination before the pregnancy, vaccination during the first trimester (LMP through week 13) of the pregnancy, vaccination during the second trimester (week 14 through week 27) of the pregnancy, vaccination during the third trimester (week 28 through term) of the pregnancy.

All secondary endpoints (serious AEFIs, pIMDs and POs) will be summarized by percentage of subjects reporting the endpoint with exact 95% CI.

CONFIDENTIAL207350 (EPI-HPV-070 VS CN PMS)
Statistical Analysis Plan**5.4.3. Additional considerations**

The percentage of subjects with at least one medically attended non-serious AEFI occurring within the 30-day (Day 1-30) follow-up period will be tabulated with exact 95% CI after any dose.

The percentage of subjects, who have used any medications, that was required to be reported as per protocol, during the whole study period will be tabulated. Medications will be coded using the GSKDRUG dictionary.

All primary and secondary endpoints (medically attended AEFIs, serious AEFIs, , casually related AEFIs , grade 3 AEFIs, pIMDs and POs) will be summarized by percentage of subjects and percentage of doses reporting the symptoms with exact 95% CI.

Incidence and nature of reported AEFIs following each dose and overall will be presented. The analysis will be done for any AEFI, medically attended AEFI within 30 days follow-up period and serious AEFI.

Adverse events will be coded using medical dictionary for regulatory activities - MedDRA classification of System Organ Class and Preferred term.

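### Pregnancy-outcome percentages pool pregnancies first reported before and after their outcome, leaving the spontaneous-abortion figure open to ascertainment bias in either direction

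*Protocol*

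**What the plan says.** Protocol 9.9.3 states: "All secondary endpoints (serious AEFIs, pIMDs and POs) will be summarized by percentage of subjects reporting the endpoint with exact 95% CI". SAP 5.4.2 carries the same rule, and SAP 5.4.3 adds that primary and secondary endpoints will be "summarized by percentage of subjects and percentage of doses reporting the symptoms with exact 95% CI". SAP 5 states that "All analyses will be performed on the exposed set". Neither document gives a denominator specific to pregnancies.

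The one planned breakdown is by exposure time. In Protocol 9.9.3, outcomes "will be summarized by the time of the vaccination, such as vaccination before the pregnancy" and then by trimester. SAP 5.4.2 dates the trimesters from the last menstrual period (LMP), for example "vaccination during the first trimester (LMP through week 13) of the pregnancy". SAP 5.4.3 also plans listings of pregnancies and infants.

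Pregnancies come to notice by several routes (Protocol 9.4): questions at vaccination visits, scheduled calls, contact started by the subject, and outside physicians. Known pregnancies are followed to their end.

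Protocol 9.12 acknowledges that there is no control group, so observed frequencies will be read against "safety data generated in clinical trials, post-licensure epidemiological studies and background incidence rates reported in the literature".

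**The concern.** SA risk is concentrated early in pregnancy. A pregnancy first reported at week 10 and still ongoing can no longer show an earlier loss. A loss that happened between two contacts enters the data only if someone mentions it. The planned percentage combines three kinds of report: ongoing pregnancies, past losses and past births. The reader cannot see how much of it rests on each. A Clopper-Pearson interval describes binomial sampling error and carries nothing about selective capture.

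This matters because the percentage will be set beside external rates that may have been ascertained differently. SA is also the outcome on which the protocol reports an open question: "data regarding the potential risk of SA, in the rare case that a woman received two doses" are described as inconclusive. The approval letter quoted in Protocol 7.1 asks for information on pregnancy outcomes.

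**Working it through.** **1. The plan's own figures.** The documents give no expected number of pregnancies and no SA figure. Their only precision figures are Tables 4 and 5 in Protocol 9.5.1. Clopper-Pearson limits reproduce every row. For example, 6/3000 gives 0.07%-0.43% and 30/3000 gives 0.68%-1.42%.

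**2. Expected exposed pregnancies.** The earlier Chinese trial had 1683 pregnancies in 6051 women (Protocol 7) over 72 months (Protocol 9.5.1).
- Rate: 1683/(6051 × 72) = 0.00386 per woman-month.
- On a 0-1-6 month schedule, the 60-day windows after doses 1 and 2 overlap (about 90 days) and dose 3 adds 60, so about 5 months in all.
- 0.00386 × 3000 × 5 ≈ 58.
- That trial enrolled women aged 18-25 and this study takes ages 9-45. If only a quarter of subjects have that rate, about 14 are expected.

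**3. Mixed entry is built into the schedule.** Call 2 falls on day 31-45 after dose 3. The next contact is Call 3, 12 months after dose 3 for on-schedule subjects, while exposure counts to day 60. A pregnancy starting on day 46-60 is first asked about (365 − 60)/7 = 43.6 to (365 − 46)/7 = 45.6 weeks after onset, when its outcome is normally known. Pregnancies found at Visits 2 and 3 or reported by the woman are often still ongoing.

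**4. Risk remaining at first report.** Assumptions, none from the documents: true SA risk 15%, spread over weeks 5-19, with the weekly hazard falling by a factor of 0.779. The risk remaining at week e is 1 − 0.85^f(e), where f(e) = (0.779^(e−5) − 0.779^15)/(1 − 0.779^15).
- Week 8: f = 0.460, so 1 − 0.85^0.460 = 7.2%.
- Weeks 6, 10 and 12: 11.8%, 4.3% and 2.5%.

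The raw percentage among pregnancies reported before outcome is thus low by construction.

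**5. Incomplete recall of earlier losses.** With first contact at week 8, the share already lost is L = 1 − 0.85/0.928 = 0.084. If a share s of those losses is captured, the crude figure is (sL + (1 − L) × 0.072)/(sL + 1 − L).

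| s | Crude SA |
|---|---|
| 100% | 15.0% |
| 70% | 12.8% |
| 50% | 11.3% |
| 0% | 7.2% |

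**6. The sign can reverse.** Let half of the known pregnancies be reported at week 8 and half after outcome, with a loss R times as likely as another outcome to be reported afterwards. Crude SA = ½ × 7.2% + ½ × 0.15R/(0.15R + 0.85).

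| R | Crude SA |
|---|---|
| 0.5 | 7.7% |
| 1 | 11.1% |
| 1.5 | 14.1% |
| 2 | 16.6% |
| 3 | 20.9% |

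Break-even is R = 1.67. Over entry weeks 6-10 and before-outcome shares of 30-80%, break-even runs from 1.1 to 7.8 and the crude figure from 5.0% to 27.8%.

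**7. Simulation on the planned contacts** (400,000 pregnancies per scenario, recognition at week 5, 0-30% self-report at recognition).
- With all past births reported, crude SA is about 6-9% if 25% of past losses are mentioned, 9-11% if 50%, and 15% if all are.
- With 90% of past losses but only 50% of other past outcomes reported, it is 16-17%.

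**8. What delayed entry costs.** With 58 pregnancies, about 32-40 are known before outcome and contribute about 1-3.5 SAs. The root-mean-square error of a delayed-entry Kaplan-Meier estimate is 7-17 percentage points, against 5-10 for the crude figure. At 50% mention, 95% of delayed-entry estimates fall within 0-53% with no self-report and 0-32% with 30%.

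**9. Denominator.** Six losses are 6/40 = 15% (5.7%-29.8%) of 40 pregnancies, but 6/3000 = 0.20% (0.07%-0.43%) of exposed subjects.

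**The case against.** The strongest reply is that this is not a registry that women join once pregnant. They enter at vaccination and are asked about pregnancy at each visit and call, so early losses belong to the cohort. If all are captured, the pooled percentage is unbiased. The weakness is then capture of past losses, not the use of a proportion. This stands. It is also why dropping after-outcome reports without a delayed-entry correction would create a downward bias of its own.

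A reader might infer that the SA percentage is biased, and most likely downward. The documents do not support that. Subjects have a phone and e-mail route, outside physicians can report suspected events, and a loss that leads to medical care may be reported more readily than an uneventful birth. Steps 6 and 7 show either sign.

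A reader might also infer that a delayed-entry estimate should be the only figure compared with background. At this size it has the larger root-mean-square error, and at 14 pregnancies it would not be usable. It also needs an independence assumption if elective terminations are censored.

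The split by vaccination timing and the listings deserve credit. They describe exposure and individual cases, however, and do not show when a pregnancy became known relative to its outcome. The caveat in Protocol 9.12 concerns rarity and the missing control group, not selective capture. The open question on SA concerns two doses only, and the change proposed here does not resolve it.

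**Conclusion.** The point holds in limited form. The planned pregnancy summaries pool reports made before and after the outcome, ignore gestational age at first report and state no per-pregnancy denominator. The SA percentage is open to ascertainment bias of unknown sign, which the exact interval does not reflect. For an assumed true risk of 15%, the simulated crude figure ran from about 6% to 17% depending only on reporting behaviour, and was correct when all past losses were captured.

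The pooling and the contact gap come from the documents. The SA risk and its shape, recognition week, self-report and mention rates are assumptions, and the pregnancy count borrows the earlier trial's rate. With 14-58 pregnancies, sampling error is also large, and the endpoint is secondary and descriptive. The priority is modest.

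**What to change.** In SAP 5.4.2:

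- Tabulate pregnancy outcomes per exposed pregnancy, overall and separately for pregnancies reported before and after the outcome was known. Show gestational age at first report and the numbers ongoing or lost to follow-up.
- For SA, keep the pooled percentage. Where numbers allow, add as a supportive sensitivity estimate the risk to week 20 among pregnancies reported before outcome, with entry at gestational age of first report. State how elective terminations are handled.
- State that the raw before-outcome percentage will not be compared with background rates without the delayed-entry correction, and that the delayed-entry estimate does not replace the crude figure as the only comparison.

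The cost is SAP wording and one extra table, with no change to study procedures. LMP is already needed for the trimester split. The date of first awareness should be recoverable, since Protocol Table 6 starts the 24-hour reporting clock from it, but the pregnancy form is not shown and this should be confirmed. The downside is a very imprecise supportive estimate.

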## **9.10. Conduct of analysis**

### **9.10.1. Sequence of analyses**

A final analysis of all data collected up to either 12 months following the third immunisation or 24 months following the first immunisation with *Cervarix* (whichever occurs first), will be conducted. This will include final analysis of safety. In case of regulatory submission before license renewal, interim report(s)/*progress report(s)* will be prepared. The statistical analyses for the interim report preparation will be performed on data collected until early 2019. The interim analyses will be described in the statistical analysis plan (SAP).

**An integrated clinical study report containing all data will be written and made available to the investigators.**

### **9.10.2. Statistical considerations for interim analyses**

Following study start, yearly progress reports (update on recruitment, follow-up status, and any other data that can be included such as simple safety description data) will be submitted to the regulatory authorities.

A comprehensive report will be prepared and submitted as part of the license renewal application process planned in **2019**. An interim analysis is anticipated for the preparation of this comprehensive report. The trigger for analysis will be the data lock point (DLP) required to meet the timelines for report preparation. Since there is no hypothesis testing, no adjustment of type I error is required. A final report will be prepared when the follow-up of all enrolled subjects has been completed.

## **9.11. Quality control**

To comply with International Conference on Harmonisation (ICH) Good Clinical Practice (GCP) or other applicable guidelines administrative obligations relating to data collection, monitoring, archiving data, audits, confidentiality, ownership and publications must be met.

### **9.11.1. Monitoring by GSK Biologicals site monitors or delegates**

- Monitoring visits by a GSK Site Monitor or delegate are for the purpose of confirming that GSK Biologicals' sponsored studies are being conducted in accordance with the ethical principles that have their origins in the Declaration of

Helsinki and that are consistent with GCP or other applicable guidelines and the applicable regulatory requirement(s) (verifying continuing compliance with the protocol, amendment(s), verifying that the site staff and facilities continue to be adequate to conduct the study).

- GSK will monitor the study to verify that, amongst others, the:
  - Data are authentic, accurate, and complete.
  - Safety and rights of study participants are being protected.
  - Study is conducted in accordance with the currently approved protocol, any other study agreements, GCP and all applicable regulatory requirements.

The investigator and the head of the medical institution (where applicable) agree to allow the monitor direct access to all relevant documents.

The investigator must ensure provision of reasonable time, space and qualified personnel for monitoring visits.

Direct access to all study-site related and source data is mandatory for the purpose of monitoring review. The monitor will perform an eCRF review and a Source Document Verification (SDV). By SDV GSK understands verifying eCRF entries by comparing them with the source data that will be made available by the investigator for this purpose.

The Source Documentation Agreement Form describes the source data for the different data in the eCRF. This document should be completed and signed by the site monitor and investigator and should be filed in the monitor's and investigator's study file. Any data item for which the eCRF will serve as the source must be identified, agreed and documented in the source documentation agreement form.

For eCRF, the monitor will freeze the screen, after she/he estimates that data are authentic, accurate and complete.

Upon completion or premature discontinuation of the study, the monitor will conduct site closure activities with the investigator or site staff, as appropriate, in accordance with applicable regulations, GCP, and GSK procedures.

### **9.11.2. Archiving of data at study sites**

Following closure of the study, the investigator must maintain all site study records (except for those required by local regulations to be maintained elsewhere) in a safe and secure location. The records must be easily accessible, when needed (e.g., audit or inspection), and must be available for review in conjunction with assessment of the facility, supporting systems, and staff. Where permitted by applicable laws/regulations or institutional policy, some or all of these records can be maintained in a validated format other than hard copy (e.g., microfiche, scanned, electronic); however, caution needs to be exercised before such action is taken. The investigator must ensure that all reproductions are legible and are a true and accurate copy of the original and meet accessibility and retrieval standards, including re-generating a hard copy, if required. Furthermore, the

investigator must ensure that an acceptable back-up of the reproductions exists and that there is an acceptable quality control procedure in place for making these reproductions.

GSK will inform the investigator/institution of the time period for retaining these records to comply with all applicable regulatory requirements. However, the investigator/institution should seek the written approval of the sponsor before proceeding with the disposal of these records. The minimum retention time will meet the strictest standard applicable to a particular site, as dictated by ICH GCP or other applicable guidelines, any institutional requirements or applicable laws or regulations, or GSK standards/procedures.

The investigator/institution must notify GSK of any changes in the archival arrangements, including, but not limited to, archival at an off-site facility and transfer of ownership of the records in the event the investigator leaves the site.

#### **9.11.3. Audits**

To ensure compliance with GCP or other applicable guidelines and all applicable regulatory requirements, GSK may conduct a quality assurance audit. Regulatory agencies may also conduct a regulatory inspection of this study. Such audits/inspections can occur at any time during or after completion of the study. The Principal Investigator has to inform GSK (study sponsor) of any external audit/inspection. If an audit or inspection occurs, the investigator and institution agree to allow the auditor/inspector direct access to all relevant documents and to allocate his/her time and the time of his/her staff to the auditor/inspector to discuss findings and any relevant issues.

### **9.12. Limitations of the research methods**

The study population may not be representative of the entire population eligible for vaccination. This is because the administration of vaccine will not be part of the universal vaccination programme but performed on a voluntary basis as per standard practice in vaccination centres. In particular, there may be an uneven age distribution of the study participants.

The study is descriptive and is not designed to assess an epidemiological association between a given adverse event and vaccination.

The sample size of approximately 3000 subjects meets the requirements of the Chinese regulation. Due to the low incidence of pIMDs (generally < 40 per 100,000) in adolescent girls and young women and the limited number of expected exposure to *Cervarix* during pregnancy, the study will be limited for the detection of these rare events.

The study will only enroll subjects vaccinated with *Cervarix* and thus will not have a control group. Therefore, the observed frequency of AEFI will be interpreted in terms of safety data generated in clinical trials, post-licensure epidemiological studies and background incidence rates reported in the literature.

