3.2 Does the protocol specify the primary and secondary (if applicable) endpoint(s) to be investigated?				32-33
3.3 Does the protocol describe the measure(s) of effect? (e.g. relative risk, odds ratio, deaths per 1000 person-years, absolute risk, excess risk, incidence rate ratio, hazard ratio, number needed to harm (NNH) per year)				

Comments:

Section 4: Source and study populations	Yes	No	N/A	Page Number(s)
4.1 Is the source population described?				18
4.2 Is the planned study population defined in terms of:				
4.2.1 Study time period?				19
4.2.2 Age and sex?				19
4.2.3 Country of origin?				19
4.2.4 Disease/indication?				16-17
4.2.5 Co-morbidity?				22
4.2.6 Seasonality?				
4.3 Does the protocol define how the study population will be sampled from the source population? (e.g. event or inclusion/exclusion criteria)				20-21

Comments:

Section 5: Exposure definition and measurement	Yes	No	N/A	Page Number(s)
5.1 Does the protocol describe how exposure is defined and measured? (e.g. operational details for defining and categorising exposure)				19
5.2 Does the protocol discuss the validity of exposure measurement? (e.g. precision, accuracy, prospective ascertainment, exposure information recorded before the outcome occurred, use of validation sub-study)				19
5.3 Is exposure classified according to time windows? (adapted as per this study design)				22

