4. ANALYSIS SETS

4.1. Exposed Set (ES)

The exposed set (ES) will include all subjects exposed to at least one dose of *Cervarix*.

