4.2.1. Elimination from Exposed Set (ES)

Code 900 (invalid informed consent or fraudulent data) and code 1030 (No administration of any dose of *Cervarix*) will be used for identifying subjects eliminated from ES

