10.1.5. Statistical methodology**10.1.5.1. Exact confidence intervals around proportions**

The exact confidence intervals around within-group proportions are derived using the method of Clopper and Pearson [[Clopper](#), 1934].

CONFIDENTIAL207350 (EPI-HPV-070 VS CN PMS)
Statistical Analysis Plan

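### Final analysis: serious AEFIs and pIMDs over the whole follow-up are planned as percentages without person-time, although they are to be read against background incidence rates

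*Protocol*

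**What the plan says.** Protocol 9.12 notes that only vaccinated subjects are enrolled, and it therefore plans an external reading of the results: "the observed frequency of AEFI will be interpreted in terms of safety data generated in clinical trials, post-licensure epidemiological studies and background incidence rates". Protocol 9.3.1.4 defines pIMDs as a subset of AEFIs, so that sentence covers them.

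The planned estimator is the same in Protocol 9.9.3 and SAP 5.4.2: "All secondary endpoints (serious AEFIs, pIMDs and POs) will be summarized by percentage of subjects reporting the endpoint with exact 95% CI". SAP 5.4.3 adds that the endpoints "will be summarized by percentage of subjects and percentage of doses reporting the symptoms with exact 95% CI", and also states: "Incidence and nature of reported AEFIs following each dose and overall will be presented". It gives no time denominator for that incidence. SAP 10.1.5.1 contains the only interval method: "The exact confidence intervals around within-group proportions are derived using the method of Clopper and Pearson". SAP section 9 has no study-specific derivations.

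Follow-up ends 12 months after dose 3 or 24 months after dose 1, whichever comes first (Protocol 9.1, SAP 3). Dose 3 may be given 5 to 12 months after dose 1. Under Table 2 of the protocol, a subject without dose 3 by month 12 is followed to month 24.

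On the denominator, SAP 4.1 says: "The exposed set (ES) will include all subjects exposed to at least one dose of" Cervarix. Under SAP 4.2.1 only codes 900 and 1030 remove a subject, so someone who withdraws early still counts in full.

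**The concern.** A background incidence rate has person-time in its denominator. The planned percentage has subjects, each followed for a different length of time. The two can be compared only after the percentage is divided by the follow-up actually accrued, and no planned output reports that quantity.

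Comparison with outside data is the only route to interpretation that the protocol names. Its authors also treat duration as material elsewhere: Protocol 9.5.1 brings a 72-month SAE percentage from the earlier Chinese efficacy trial (HPV-039) down to this study's shorter follow-up in order to size the study. The observed data get no such treatment. A reader of the final report would have to guess mean follow-up before setting the serious-AEFI or pIMD result beside a published rate.

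**Working it through.** **Reproducing the plan's figures.** Protocol 9.5.1 takes 1.9% over 72 months and assumes 0.5% here, on at least 18 months of follow-up. Linear scaling gives 1.9% × 18/72 = 0.475%, which rounds to 0.5%. Table 5 gives 15/3000 = 0.50% with limits 0.28% to 0.82%, and Clopper–Pearson returns 0.280% to 0.823%. Both reproduce.

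**Range of follow-up.**
- Shortest for a completer on schedule: 5 + 12 = 17 months.
- Longest in the main window: 24 months. Ratio 24/17 = 1.41.
- Withdrawals: the documents give no rate. Assume that 10% or 20% leave at month 6 on average and the rest are followed for 18 months. Mean follow-up is 0.9 × 18 + 0.1 × 6 = 16.8 months, or 0.8 × 18 + 0.2 × 6 = 15.6 months. The mean can therefore fall below 17 months.

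**Person-years for 3000 subjects** (3000 × months/12): 3900 at 15.6 months, 4500 at 18, 6000 at 24.

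**Zero pIMDs observed.** The exact binomial upper limit is 1 − 0.025^(1/3000) = 0.1229%, or 123 per 100,000 subjects. The exact Poisson upper limit on the count is −ln(0.025) = 3.689. Divided by person-years:

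| Mean follow-up | Person-years | Upper limit per 100,000 person-years |
|---|---|---|
| 15.6 months | 3900 | 95 |
| 18 months | 4500 | 82 |
| 24 months | 6000 | 61 |

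The same percentage corresponds to any of these, and the planned output does not say which.

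**Fifteen serious AEFIs (the plan's own 0.50%).** Rate = 15/person-years, with exact Poisson 95% limits:

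| Mean follow-up | Rate per 100,000 person-years | 95% CI |
|---|---|---|
| 15.6 months | 385 | 215–634 |
| 18 months | 333 | 187–550 |
| 24 months | 250 | 140–412 |

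**Size relative to sampling error.** Across these means the rate moves by a factor of 24/15.6 = 1.54. Within any one row the upper limit is about 2.9 times the lower (for example 550/187). Sampling error is the larger of the two.

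**Expected pIMDs.** Protocol 9.12 gives a background generally below 40 per 100,000 and states no time unit. If it is per year and covers all pIMDs combined (both assumptions), using 40 as the rate gives 40/100,000 × 3900, 4500 or 6000 = 1.6, 1.8 or 2.4 expected cases.

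**The case against.** The strongest reply is that the study is descriptive, tests no hypothesis, and says in 9.12 that it cannot assess association or detect rare events well. Background rates are one of three comparators named. With about two pIMDs expected, a rate will have a very wide interval. Withdrawals and doses received are tabulated, so a reader could approximate the follow-up. Table layouts are in a separate document (SAP 10.2) that is not available here, so a rate table cannot be ruled out. All of this stands, and it limits the weight of the point. It does not remove the gap: a descriptive result should be on the scale of what it will be read against, approximation is unnecessary when the dates are held, and the SAP gives no method for a rate.

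Item 3.3 of the ENCePP checklist in Protocol Annex 10, on measures of effect, lists person-years among its examples and is marked not applicable. That fits a study without a comparator and is weak evidence either way.

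Three stronger readings are tempting, and the documents do not support them.
- **That the conclusion on serious AEFIs turns on mean follow-up.** HPV-039's 1.9% over six years is about 317 per 100,000 person-years, and 15/3000 crosses that value at 18.9 months. This is circular: 15/3000 is the HPV-039 figure scaled to 18 months and rounded up, and 18 × 0.50/0.475 = 18.9. All three intervals in the table contain 317.
- **That a rate makes the comparison fully like-for-like.** HPV-039 is given as a percentage, so a constant-rate assumption is still needed. The pIMDs of interest also include exacerbations (Protocol section 7), whereas background incidence ordinarily counts new onset.
- **That the sponsor will set a 17–24-month percentage directly against an annual rate.** No passage plans that.

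**Conclusion.** The point holds as an inexpensive improvement to the final analysis. The plan names background incidence rates as a comparator but plans no output with a time denominator, although follow-up varies by design and withdrawals remain in the denominator. Depending on mean follow-up, the upper limit for zero pIMDs is 61 to 95 per 100,000 person-years, where the planned output would show only 123 per 100,000 subjects.

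Those figures assume 3000 subjects, the withdrawal pattern stated above for 15.6 months, and everyone followed for the stated mean in the other rows. The actual value cannot be derived from the documents. The gain is comparability, not precision. Nothing here shows an error in the plan's own numbers. The interim reports refer to a separate analysis request and are outside this point.

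A separate minor matter: Protocol 9.1 and 9.5.1 and SAP 3 give completers at least 18 months of follow-up, while the 5-month lower limit for dose 3 plus 12 months gives 17. At 17 months the serious-AEFI assumption would be 1.9% × 17/72 = 0.449% instead of 0.475%, a negligible difference. The passages still need to be reconciled.

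**What to change.** In SAP 5.4.2 keep the percentages. For the final analysis add, separately for serious AEFIs and for pIMDs:
- total person-years, and the rate of first events per 100,000 person-years with an exact Poisson 95% CI, with the method added to SAP 10.1.5;
- time at risk from dose 1 to the earliest of first event, completion or withdrawal date, or the end of the main window (12 months after dose 3 or 24 months after dose 1). The cap is needed because study conclusion for subjects in pregnancy follow-up comes when the child is about 12 months old;
- a rule that infant events and congenital anomalies do not enter the serious-AEFI rate. Protocol 9.3.1.3 counts congenital anomalies as serious and SAP 10.1.3.3 already separates infant events; report them separately as planned;
- new-onset pIMDs shown apart from exacerbations wherever background incidence is the comparator.

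Rows by age are optional and would be too imprecise to show differences in pIMDs.

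The cost is a few table rows with wide intervals. SAP 7.1 already uses administration, onset and completion or withdrawal dates. The SAP is dated 4 November 2020, before the planned end of data collection in the first quarter of 2021. Any comparison with HPV-039 should state its constant-rate assumption.

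Separately, reconcile the 18-month minimum follow-up with the dose 3 window in both documents.
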